Data collection will be performed at baseline (Pfizer-BioNTech COVID-19 mRNA vaccine dose received at index date), and at weeks 1, 2, 4, 6, 8, 12 and every three months thereafter, through 24 months following index date (or until the occurrence of death, withdrawal of consent, loss to follow-up, or end of study period, whichever occurs first). In addition, data will be collected on any subsequent vaccine doses received during the study period. If a participant receives a subsequent Pfizer-BioNTech COVID-19 mRNA vaccine dose during the study period, the data collection schedule will reset based on the reported date of subsequent vaccine dose, with data collected at weeks 1, 2, 4, 6, 8, 12 and every three months thereafter from the reported date of subsequent vaccine dose only. If a participant receives another COVID-19 vaccine (**not** the Pfizer-BioNTech COVID-19 mRNA vaccine) dose during the study period, the data collection schedule will not reset, but the participant will remain in the study and the follow-up schedule will continue based on the previous Pfizer-BioNTech COVID-19 mRNA vaccine date. The observation period will not be extended if subsequent doses are received; the observation period will remain at 24 months following baseline (vaccination dose received at index date), or until the occurrence of death, withdrawal of consent, loss to follow-up, or end of study period, whichever occurs first.

An overview of the data collection schedule is shown in [Figure 1](#).

Figure 1. Data Collection Schedule

¹ Index Dose can be Dose 1, Dose 2 or Booster/Additional Dose

Participants may also report medically attended safety events of interest at any time outside of regular survey follow-up, via the participant portal within the study website or mobile app, or to the IQVIA call center.

Participant reported medically attended safety events of interest will be confirmed by the treating HCPs or through medical record documentation if needed to validate or establish the diagnosis associated with the event and validate the occurrence of a safety event of interest, or other clinically significant events. This process is further detailed in [Section 10](#).

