9.4. Data sources

Scheduled assessments for the study are presented in the Data Collection Schedule provided in [Table 3](#) below. Participant informed consent must be obtained before any data are collected.

Baseline data will be collected via an electronic Case Report Form (eCRF). At baseline, data listed in [Section 9.4.1](#) will be collected directly from the persons receiving the vaccine and/or their designee; this may include HCP or study staff administering the vaccine. Data describing vaccine administration on that date will also be collected.

For follow-up data, standard questionnaires will be completed by participants or their designees online or via the mobile app. The data listed in [Section 9.4.2](#) will be collected. Telephone interviews will use a standard script for interviews. Both data collection methods will include information that reported medically attended safety events of interest and laboratory confirmed COVID-19 infections may trigger additional follow-up to obtain further information.

Participant reported medically attended safety events of interest will be reviewed and additional safety data will be collected from HCPs if needed to validate or establish the diagnosis associated with the event and validate the occurrence of the reported safety event or other clinically significant events. A standard questionnaire will be used for this follow-up.

Participants will be asked to report any subsequent COVID-19 vaccine received during the follow-up period. The data to be collected is listed in [Section 9.4.3](#).

If the participant fails to submit follow-up data / is non-responsive to follow-up reminders or telephone calls, follow-up with a secondary contact will be conducted (as per [Section 9.2.3](#)) in order to determine whether non-response is due to a safety event of interest.

Table 3. Data Collection Schedule.

	Baseline	Each subsequent vaccine dose	Follow-up at weeks 1, 2, 4, 6, 8 and 12 following each Pfizer-BioNTech COVID-19 mRNA vaccine dose	Quarterly follow-up until 24 months following index date, or end of study, whichever occurs first
Informed consent	X			
Demographics	X			
Medical history	X	X		
Concomitant medication and other vaccines	X	X		
Pfizer-BioNTech COVID-19 mRNA vaccine information	X	X		
Pregnancy status (if applicable)	X	X	X	X
Occurrence of medically attended safety events of interest			X	X
Pregnancy outcomes (if applicable)			X	X
Contact information and preferred follow-up method	X	X	X	X

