9.4.2. Weekly, monthly, and long-term follow-up, through 24 months following the index date vaccine dose

The following data will be collected directly from participants at pre-specified follow-up points outlined in the data collection schedule (further details in [Annex 3](#)):

1. Pregnancy status (female participants of childbearing potential only), and pregnancy outcomes (as applicable).
2. Details of medically attended safety events of interest, including laboratory confirmed diagnosis of COVID-19, since the last follow-up.
3. Any changes in contact information.
4. Changes in preferred follow-up method – telephone interview or web/app-based questionnaire.
5. Discontinuation data will be collected for all enrolled participants at the time of discontinuation:
 - Date of discontinuation.
 - Number of vaccine doses received at the time of discontinuation.
 - Reason for discontinuation.

Data on reactogenicity will be collected only during week 1 following each Pfizer-BioNTech vaccine dose.

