Time at risk will be assessed from the Pfizer-BioNTech COVID-19 mRNA vaccine dose until the subsequent follow-up time point or until the next Pfizer-BioNTech COVID-19 mRNA vaccine dose received, death, withdrawal of consent, loss to follow-up, 24 months or end of study period, whichever occurs first. Sensitivity analysis may be conducted with censoring at any COVID-19 vaccine dose received.

All cases of reported laboratory confirmed COVID-19 in the study population will be described by the Brighton Collaboration “Vaccine-associated Enhanced Disease” Working Group case definitions for COVID-19 VAED.

Counts of newly reported medically attended safety events of interest and counts of vaccinated participants will be summarized as per the intervals above. Counts will be summarized by whether medical validation of the event was possible, or not.

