18.1.2. Each subsequent COVID-19 vaccine dose questionnaire

- Vaccination information:
 - Manufacturer
 - Date of vaccination
- Pregnancy status (female participants of childbearing potential only)

⁶ https://www.bgs.org.uk/sites/default/files/content/resources/files/2018-05-23/fff_full.pdf

- Any changes in contact information
- Any changes in preferred participant follow-up method

The following additional fields completed if the vaccine received is the Pfizer-BioNTech COVID-19 mRNA vaccine:

- Additional vaccination information:
 - Location (i.e. vaccination center)
 - Vaccine lot number
 - Anatomical site where vaccine was administered
- Any changes in prior submitted medical history
 - Any concomitant medication taken within 7 days prior to vaccination (*Drugbank coded*)
 - Any other vaccinations (other than the COVID-19 vaccine, and other than any previously reported) in the last 6 months
 - Presence of potential active viral disease within previous 3 days prior to vaccination (e.g. fever, symptoms of cold, flu, or other inflammatory/infectious process)

18.1.3. Safety outcome follow-up questionnaire (weekly, monthly, and long-term follow-up, through 24 months following the index date vaccine dose)

In addition to discontinuation data being collected during follow up (discontinuation date, number of vaccine doses received by discontinuation, and discontinuation reason), outcome follow up will include:

- Pregnancy status (female participants of childbearing potential only)
- Have you received any non-routine (unplanned) medical care since your vaccination / last follow-up questionnaire? (*with the below options to be tailored for each country*)
 - Yes – primary care physician / general practitioner
 - Yes – emergency department
 - Yes – hospital (inpatient)
 - Yes – hospital (outpatient)
 - Yes – Intensive Care Unit or High Dependency Unit
 - No

If a participant selects yes to any of the above, they will be asked how many events they need to report, and asked to complete all of the following questions for each event:

- What was the main purpose of your non-routine (unplanned) medical care?
 - I have been diagnosed with this condition in the past, but my symptoms changed or got worse
 - I experienced new symptoms and was diagnosed with this condition for the first time
- Relevant details will be collected:
 - Date of visit
 - Date of end of visit (if applicable)

- Details of HCP (as minimum: name, location, email)

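### After a later Pfizer-BioNTech dose resets the questionnaire schedule, no closing contact is named at the end of observation, so up to about 3 months of counted time at risk can have no scheduled safety question

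*Protocol*

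**What the plan says.** Protocol section 9.1 sets contacts at "weeks 1, 2, 4, 6, 8, 12 and every three months thereafter" after the index dose. If a later Pfizer-BioNTech dose is received, the schedule restarts and runs "every three months thereafter from the reported date of subsequent vaccine dose only". A dose of another manufacturer's COVID-19 vaccine does not restart it. The end of observation does not move: "The observation period will not be extended if subsequent doses are received".

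Section 9.7 starts time at risk at a Pfizer-BioNTech dose. It ends at the following contact point or until the next Pfizer-BioNTech dose "received, death, withdrawal of consent, loss to follow-up, 24 months or end of study period, whichever occurs first".

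In Table 3 (section 9.4), the row "Occurrence of medically attended safety events of interest" is marked for the weekly and quarterly contacts but not for the subsequent-dose column. The quarterly column gives month 24 or end of study as a limit, not as a contact.

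On recall, section 9.4.2 asks at each follow-up for safety events "including laboratory confirmed diagnosis of COVID-19, since the last follow-up". The Annex 3 item in section 18.1.3 asks: "Have you received any non-routine (unplanned) medical care since your vaccination / last follow-up questionnaire". Section 9.1 also lets participants report events at any time outside the schedule.

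**The concern.** Questionnaires are anchored to the latest Pfizer-BioNTech dose, while the end of observation is anchored to the index dose. When the interval between the two doses is not close to a whole number of quarters, the last questionnaire falls before month 24 and the next would fall after observation has closed. Nobody is asked about the time in between, yet it stays in the denominator.

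If events in that stretch are reported less completely than solicited events, the primary incidence rates are too low. The observed count in the observed-to-expected analysis is also too low against an expected count built on the full person-time. Both errors point towards apparent safety. The effect is strongest in the last reporting interval, where none of the person-time after the last contact has a scheduled question behind it. A statistical analysis plan cannot repair this later, because it cannot recover answers to a form that was never sent.

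**Working it through.** **The plan's own figures.** The protocol gives no figure for uncovered time. Its enrolment target reproduces: 10,000 / (1 - 0.25) = 13,333.3, rounded up to 13,334. The point does not depend on it.

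**Inputs.** The contact schedule, the reset rule and the fixed end come from section 9.1; the end of time at risk comes from section 9.7. Assumptions: one month = 365.25/12 = 30.44 days, so 24 months = 730.5 days and one quarter = 91.3 days. The quarterly contacts can be read in two ways: (A) week 12 plus whole quarters, or (B) months 6, 9, 12 and so on from the dose. Both were run.

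**Formula.** For a later dose on day d, tail = 730.5 minus the last contact day that is not after 730.5. On whole months this is close to (24 - t) mod 3 for a dose at month t.

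**No reset.** A: last contact at 84 + 7 x 91.3125 = 723.2 days, tail 7.3 days. B: last contact at month 24, tail 0.

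**Second dose at an assumed 3 weeks (day 21).** B: last contact at 21 + 639.2 (21 months) = 660.2; tail 70.3 days, about 10 weeks, and 70.3/730.5 = 9.6%. A: last contact at 21 + 84 + 6 x 91.3125 = 652.9; tail 77.6 days, about 11 weeks.

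**Booster at month 7 (reading B).** Quarterly points fall at months 10 (as the week 12 form, a week earlier), 13, 16, 19 and 22. The next would be month 25, so months 22 to 24 have no contact.

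| Later dose at month | Tail, reading A (days) | Tail, reading B (days) |
|---|---|---|
| 3, 6, 9 or 12 | 7.3 | 0 |
| 4 or 7 | 68.2 | 60.9 |
| 5 or 8 | 37.8 | 30.4 |

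**All dose days from 21 to 730, evenly weighted.** The largest tail is 91.25 days under A (12.5% of 730.5) and 98.5 days under B (13.5%). The mean is 40.7 days under A and 41.7 under B, so about 41 days: 41/730.5 = 5.6%. The tail exceeds 30 days for about 59% of dose days and 60 days for about 29 to 30%.

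**Effect on a rate.** With a constant event rate, and a fraction u of tail events never reported, the rate in a re-dosed participant falls on average by 5.6% x u: 0 if every tail event is volunteered, 5.6% if none is. The protocol gives neither u nor the share of participants who will be re-dosed.

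**Cut-off by end of study.** Section 6 gives data collection from 31 August 2021 to 31 October 2023, about 26 months. If that end date closes observation, anyone with an index date after 31 October 2021 stops before month 24. From 7 January 2022, the date of version 4.0, only about 21.7 months remain. Such a participant stops wherever the date falls between two quarterly contacts, reset or not.

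**The case against.** **Section 9.7 ties time at risk to contact points.** It does, but it takes whichever stop comes first. When the next contact would be month 25, month 24 comes first, so the stretch from month 22 is counted. One could instead read the sentence as ending at the last contact that actually occurs. The bias then disappears, but the final weeks of the promised 24 months go unobserved. Either way a closing contact is needed.

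**A final contact may be implied.** Several passages describe collection through 24 months, section 9.7.1 mentions reporting windows around target timepoints, and Figure 1 could not be seen. The fair statement is therefore that the visible text names no closing contact. A window around a contact does not create one at month 24, and the word only in section 9.1 excludes falling back on the index-based schedule.

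**Participants can report at any time.** This reduces the loss and stands as mitigation. It does not replace solicitation in a study titled active surveillance, and section 9.9 accepts that events between questionnaires may go unreported.

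**The size is modest.** This stands. A mean of 5.6% in re-dosed participants is below Table 4's relative margin at 25% attrition for every rate up to 500 per 10,000 person-years (29.0/500 = 5.8%; 20.5/250 = 8.2%). The dense contacts just after each dose, which matter most for acute events, are protected by the reset. But a downward bias is not removed by a wide interval, and it is cheap to prevent.

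**Conclusion.** The tail gap holds. After a reset, 0 to about 3 months of counted time at the end of observation has no scheduled safety question. The mean is about 41 days (5.6% of 24 months) if later doses are spread evenly, and about 10 weeks for a second dose at an assumed 3 weeks. The bias in rates and observed-to-expected ratios is downward. Its size depends on how many tail events are volunteered and how many participants are re-dosed, neither of which the protocol states.

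Three stronger readings are tempting but not supported:

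- A reader might infer from Table 3 and the 18.1.3 item that the weeks just before a new dose are never asked about. Section 9.4.2 and the abstract's variables section have every follow-up form look back to the last follow-up, so the week 1 form after the new dose covers them. What remains is loose wording in 18.1.3. The exception is a dose in the last week before month 24, after which no further contact falls. It follows that a pre-dose gap cannot be added to the tail to make a fixed 3-month loss.
- A reader might infer that every reset leaves a gap. A later dose near a multiple of three months leaves 0 to about 7 days.
- A reader might infer that only re-dosed participants are affected. Anyone stopped by the end of study between contacts has the same kind of tail.

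**What to change.** In section 9.1 and Table 3, add a closing safety questionnaire at index + 24 months or end of study, whichever comes first, for every participant still in follow-up, whatever the reset date. Once completed, it reduces the tail to zero for every dose date and also covers those cut off by the end of study.

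As a minor addition, in section 18.1.3 make the recall start the last completed questionnaire on every form except the first after index. This agrees with section 9.4.2 and leaves no doubt that the week 1 form after a new dose covers the weeks before it.

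The cost is one extra short questionnaire for each participant whose schedule does not already end at that point, plus a form-text change. Ending time at risk at the last completed questionnaire may be run as a sensitivity analysis, but it is not part of this change: it would alter censoring more widely, including for the uncontactable participants whom section 10.3 keeps in follow-up.

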9.2. Setting

This primary data collection study will aim for up to 10,000 vaccine recipients with 2 years of follow-up data. In order to reach this estimated sample size of vaccine recipients with complete data, 13,334 participants will be targeted for enrolment, assuming a 25% dropout rate over the 2-year follow-up period. The study will be conducted in Germany, Italy and Spain in a total of approximately 20 centers. Other countries may be included in addition to, or as a replacement, for one or more of these countries, as required to fulfill study objectives.

It is anticipated that participants will be enrolled from settings based upon the regional availability and distribution of vaccine according to national or regional COVID-19 preparedness plans and may include physician offices, hospitals, pharmacies, and/or vaccination centers. Site selection criteria will include the projected availability of eligible participants in the enrolment period and the availability of physician (and other site staff) time to complete brief baseline case report forms (CRFs) where required. Selection criteria and basic site information (e.g. site size, site type) will be collected via a site qualification survey.

Limited inclusion/exclusion criteria will be applied in this study, to ensure comprehensive capture of individuals receiving the Pfizer-BioNTech COVID-19 mRNA vaccine in real-world settings.

Participants will be considered enrolled if they meet the inclusion/exclusion criteria below, have provided informed consent (as required per local regulations), and have reported the date of Pfizer-BioNTech COVID-19 mRNA vaccination at baseline.

9.2.1. Inclusion criteria

Participants must meet all of the following inclusion criteria to be eligible for inclusion in the study:

1. Participant's age is 18 years and above, and in accordance with the approved product label of the country where the study is conducted.
2. Enrolment within 5 days of receipt of any dose (i.e. first, second, or any subsequent booster dose) of the Pfizer-BioNTech COVID-19 mRNA vaccine.

Note:

Heterologous primary vaccination (two different COVID-19 vaccines [different manufacturers] received for the first and second doses of a primary [initial] course) and heterologous boosting (a third dose of a different manufacturers COVID-19 vaccine as a booster 3 to 6 months after a primary vaccination course) are now commonplace.

Individuals receiving heterologous booster doses are allowed to enroll in this study, if the booster dose received is the Pfizer-BioNTech COVID-19 mRNA vaccine. However, if a participant is enrolling at second Pfizer-BioNTech COVID-19 mRNA vaccine dose, the first dose received must have also been the Pfizer-BioNTech COVID-19 mRNA vaccine². If a participant is enrolling at second or booster dose of Pfizer-BioNTech COVID-19 mRNA vaccine, the participant must be able to provide the date and manufacturer of all previous COVID-19 vaccine doses received in order to be eligible for inclusion.

3. Adult participants willing to provide informed consent according to local regulations and complete all study procedures in accordance with the protocol, including consent for the study team to contact the treating HCP or healthcare facility to obtain additional information related to safety events reported by the participant.

² Including patients receiving the Pfizer-BioNTech COVID-19 mRNA vaccine as their second dose, who have not received the Pfizer-BioNTech COVID-19 mRNA vaccine as their first dose, would result in any vaccine effects being difficult to distinguish between manufacturers. No such restrictions are placed upon participants enrolling at booster doses, as the time window between doses is anticipated to be longer, with reduced likelihood of overlapping risk intervals.

9.2.2. Exclusion criteria

Participants will be excluded from the study if they do not meet the inclusion criteria or have prior receipt of any investigational COVID-19 vaccination.

9.2.3. Recruitment and retention

After vaccination, all eligible individuals will be invited to participate in the study within 5 days of vaccination, and will be fully informed about the nature and objectives of the study, as well as the sharing of data relating to the study. The study recruitment strategy will encourage enrolment within 2 days of vaccination. Individuals will be provided adequate time to have questions answered prior to consenting to participate. Further details of the consent process are detailed in [Section 9.2](#). All participants will be able to withdraw consent at any time via the app, or at any follow-up point via telephone.

Participants will be followed up at pre-specified, regular intervals. As described in [Section 9.1](#), participants will have the opportunity to choose their preferred method of follow-up. Reminders will be sent if a participant fails to submit follow-up data via the app, and follow-up calls will be attempted if a participant fails to submit follow-up data via telephone. If the participant is non-responsive to follow-up reminders or telephone calls, follow-up with a secondary contact and the participant's primary care will be attempted, in order to determine whether non-response is due to a safety event of interest.

For participants who request to participate via the app, the following reminder schedule will be implemented:

For the weekly and bi-weekly questionnaires completed as needed after each dose:

- Two digital reminders,
- If digital reminders are ignored by the participant, the IQVIA call center will call to remind the participant to complete the questionnaire, as well as offer a Toll Free Number (TFN) if the participant would prefer to complete the questionnaire over the phone by talking to an agent,
- If no response to the call center or call-in to TFN, the named secondary contact provided by the participant will be contacted,

For the quarterly questionnaires after each dose:

- Three digital reminders,
- If digital reminders are ignored by the participant, the IQVIA call center will call to remind the patient to complete the questionnaire, as well as offer a TFN if the participant would prefer to complete the questionnaire over the phone by talking to an agent,
- If no response to the call center or call-in to TFN, the named secondary contact provided by the participant will be contacted,

For participants who indicate a phone call as their preferred method of follow-up, the reminder schedule will be similar to the approach described above, but rather than the initial digital reminders, the first follow-up attempts will be via the call center. If these are ignored, the call center will phone the named secondary contact.

